Cohort 1: AAV5-hFIX 5.0 x 10^12 gc/kg, Cohort 2: AAV5-hFIX 2.0 x 10^13 gc/kg Adverse Events coded with MedDRA version 17.1

UniQure/AMT/CT-AMT-060-01/current - tab\_ae.sas/tab\_ae\_teae\_mod.rtf/10jan2018

x (x.xx) x

x (x.xx) x

Sponsor: uniQure biopharma B.V	Date 27MAY2021			larix
Trial ID: CT-AMT-060-01 EudraCT No: 2013-00557942-42	Table Shells			Final Version 05 Page 51 of 66
Table 14.3.1.8 Frequency and Incidence of Th	EAEs of Severe Severity by MedDRA SOC :	and PT - Full analy	sis set	
SOC PT	Cohort 1 (N=x) n (%) E	Cohort 2 (N=x) n (%) E	Total (N=x) n (%) E	
Any severe TEAEs	x (x.xx) x	x (x.xx) x	x (x.xx) x	
Nervous system disorders Myelopathy	x (x.xx) x x (x.xx) x	x (x.xx) x x (x.xx) x	x (x.xx) x x (x.xx) x	

TEAE: Treatment Emergent Adverse Event. MedDRA: Medical Dictionary for Regulatory Activities. SOC: System Organ Class. PT: Preferred Term.

N: Number of patients in Full Analysis Set (FAS). n: Number of patients with events. (%): Percentage of patients in FAS with Adverse Event. E: Number of Adverse Events.

Cohort 1: AAV5-hFIX 5.0 x 10^12 gc/kg, Cohort 2: AAV5-hFIX 2.0 x 10^13 gc/kg

Adverse Events coded with MedDRA version 17.1

Sponsor: uniQure biopharma B.V

Date 27MAY2021

Trial ID: CT-AMT-060-01 EudraCT No: 2013-00557942-42

Table Shells

Table 14.3.1.9 Frequency and Incidence of TEAEs Leading to Discontinuation by MedDRA SOC and PT - FAS

As 14.3.1.8

Sponsor: uniQure biopharma B.V	Date 27MAY2021			larix
Trial ID: CT-AMT-060-01 EudraCT No: 2013-00557942-42	Table Shells			Final Version 05 Page 53 of 66
Table 14.3.1.10 Frequency and Incidence of TEAEs Qualifying	for Special Notification	by MedDRA SOC ar	nd PT - FAS	
SOC PT	Cohort 1 (N=x) n (%) E	Cohort 2 (N=x) n (%) E	Total (N=x) n (%) E	
Any TEAEs qualifying for special notification	x (x.xx) x	x (x.xx) x	x (x.xx) x	
Investigations Transaminases increased	x (x.xx) x x (x.xx) x	x (x.xx) x x (x.xx) x	x (x.xx) x x (x.xx) x	
Alanine aminotransferase increased	x (x.xx) x x (x.xx) x	x (x.xx) x x (x.xx) x	x (x.xx) x x (x.xx) x	
General disorders and administration site conditions Drug ineffective	x (x.xx) x x (x.xx) x	x (x.xx) x x (x.xx) x	x (x.xx) x x (x.xx) x	
Psychiatric disorders Anxiety	x (x.xx) x x (x.xx) x	x (x.xx) x x (x.xx) x	x (x.xx) x x (x.xx) x	

TEAE: Treatment Emergent Adverse Event. MedDRA: Medical Dictionary for Regulatory Activities. SOC: System Organ Class. PT: Preferred Term.

N: Number of patients in Full Analysis Set (FAS). n: Number of patients with events. (%): Percentage of patients in FAS with Adverse Event. E: Number of Adverse Events. Cohort 1: AAV5-hFIX 5.0 x 10^12 gc/kg, Cohort 2: AAV5-hFIX 2.0 x 10^13 gc/kg

Adverse Events coded with MedDRA version 17.1

Sponsor: uniQure biopharma B.V	Date 27MAY2021	larix
Trial ID: CT-AMT-060-01 EudraCT No: 2013-00557942-42	Table Shells	Final Version 05 Page 54 of 66

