13.1 Adverse Event Definitions

An adverse event (AE), an adverse drug reaction (ADR) and a serious adverse event (SAE) are defined according to [ICH Guideline E2A](#).

An AE is any untoward medical occurrence in a subject administered the IMP and which does not necessarily have a causal relationship with this IMP or the IMP administration procedure. An AE can therefore be any unfavourable and unintended sign (including an abnormal laboratory finding, see [Section 12.4](#)), symptom, or disease temporally associated with the use of the IMP including the IMP administration procedure.

An ADR is an untoward and unintended response to the IMP related to any dose administered. A causal relationship between the IMP and the AE is at least a reasonable possibility.

An SAE is any untoward medical occurrence that at any dose:

- Results in death
- Is life-threatening (this refers to an event in which the subject was at risk of death at the time of the event; it does not refer to an event that hypothetically might have caused death if it was more severe)
- Requires in-patient hospitalization or prolongation of existing hospitalization
- Results in persistent or significant disability or incapacity
- Is a congenital anomaly or birth defect
- Is judged medically important by the Investigator (this refers to an event, not resulting in any of the outcomes listed above, but may jeopardize the subject or may require intervention to prevent one of the other outcomes listed)

In the following situations, events are not defined as an AE:

- Medical or surgical procedure (e.g. endoscopy, appendectomy); the condition that leads to the procedure is an AE
- Anticipated day-to-day fluctuations of pre-existing disease(s) or condition(s) present or detected at the start of the trial that do not worsen
- Condition(s) for which pre-planned procedure(s) have been recorded at Visit 1, including hospitalization(s), unless the condition(s) for which the procedure and/or hospitalization was planned has worsened from the first trial related activity after the subject has signed the informed consent form
- Concomitant illness identified during the screening procedures will be recorded as medical history. However, whenever symptoms for these condition(s) worsen and/or become serious, then these events must be reported as an AE or SAE, as applicable.

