13.2.2 Relationship to IMP

Assessment of causality is based on the following considerations: associative connections (time and/or place), pharmacological explanations, previous knowledge of the drug, presence of characteristic clinical or pathological phenomena, exclusion of other causes, and/or absence of alternative explanations.

The Investigator will be asked to assess causal relationship to the trial treatment according to the following classifications:

- *Probably related*: An AE with a reasonable time sequence to administration of the IMP, unlikely to be attributed to concurrent disease or other drugs or chemicals, and which follows a clinically reasonable response on withdrawal (de-challenge). Re-challenge information is not required to fulfil this definition.
- *Possibly related*: An AE with a reasonable time sequence to administration of the IMP, but which could also be explained by concurrent disease or other drugs or chemicals. Information on drug withdrawal may be lacking or unclear.
- *Unlikely related*: An AE with a temporal relationship to IMP administration which makes a causal relationship improbable, and in which other drugs, chemicals or underlying disease provide plausible explanations.
- *Not applicable*: This assessment can be used e.g. in cases where the subject did not receive any treatment with IMP.

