# 4.5.1 Adverse Events – Primary Safety Endpoint

All reported adverse events will be coded using the Medical Dictionary for Regulatory Activities (MedDRA version 17.1).

An AE is considered related with the use of drug if the relationship to IMP is classified as either 'Probably related' or 'Possibly related'. A related AE is referred to as an Adverse Drug Reaction (ADR).

An adverse event is defined as treatment emergent (TEAE) when onset of the event is after the administration of the IMP. In case an AE starts the same day of IMP administration and the exact time is missing, it will be defined as Treatment Emergent AE.

Adverse events for special notification are determined through the eCRF.

In case of missing or incomplete onset dates of AEs the onset date will be imputed such that the event starts as early as possible based on the partial date. Furthermore, if the AE could be treatment emergent based on the missing or incomplete date, then the AE will be regarded as treatment emergent.

Furthermore, missing values for AEs will be treated as missing except for causality and intensity. If causality is missing for a TEAE, the TEAE will be regarded as 'Probably related'. If causality is missing for an AE with onset before administration of trial drug, the AE will be regarded as 'Unlikely related'. If the intensity is missing the intensity of the AE will be regarded as severe. In case seriousness is missing this should be queried again since seriousness cannot be imputed as 'Yes' by default, since this would affect the reconciliation between trial data base and registry of SAEs.

All TEAEs will be tabulated, while pre-treatment AEs will only be listed.

An AE overview summary table will be prepared including the number of patients reporting at least one AE, the percentage of patients (%) with at least one AE, and the number of events (E) reported, for the following categories:

- TEAEs
- Related TEAEs
- Deaths
- Serious TEAEs
- Severe/Moderate/Mild TEAEs
- TEAEs leading to discontinuation of study treatment (defined as action taken='Drug withdrawn' on the AE form)
- TEAEs qualifying for special notification

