14.3.1 Displays of Adverse Events

Sponsor: uniQure biopharma B.V	Date 27	MAY2021	a	irix
Trial ID: CT-AMT-060-01 EudraCT No: 2013-00557942-42	Table	Shells	Final V Page	ersion 05 38 of 66
Table 14.3.1.1 Overall Summary of Treatme	ent Emergent Adverse Event	s - FAS		
	Cohort 1 (N=x) n (%) E	Cohort 2 (N=x) n (%) E	Total (N=x) n (%) E	
All TEAEs	x (xx.x) x	x (xx.x) x	x (xx.x) x	
Mild TEAEs	x (xx.x) x	x (xx.x) x	x (xx.x) x	
Moderate TEAEs	x (xx.x) x	x (xx.x) x	x (xx.x) x	
Severe TEAEs	x (xx.x) x	x (xx.x) x	x (xx.x) x	
Probably Related TEAEs (ADRs)	x (xx.x) x	x (xx.x) x	x (xx.x) x	
Possibly Related TEAEs (ADRs)	x (xx.x) x	x (xx.x) x	x (xx.x) x	
Unlikely Related TEAEs (ADRs)	x (xx.x) x	x (xx.x) x	x (xx.x) x	
Serious TEAEs (SAEs)	x (xx.x) x	x (xx.x) x	x (xx.x) x	
Deaths	x (xx.x) x	x (xx.x) x	x (xx.x) x	
TEAEs leading to discontinuation	x (xx.x) x	x (xx.x) x	x (xx.x) x	
TEAEs for special notification	x (xx.x) x	x (xx.x) x	x (xx.x) x	

TEAE: Treatment Emergent Adverse Event. ADR. Adverse Drug Reaction.

N: Number of patients in Full Analysis Set (FAS). n: Number of patients with events. (%): Percentage of patients in FAS with Adverse Event. E: Number of Adverse Events.

Cohort 1: AAV5-hFIX 5.0 x 10^12 gc/kg, Cohort 2: AAV5-hFIX 2.0 x 10^13 gc/kg

Sponsor: uniQure biopharma B.V	Date 27MAY2021			arix
Trial ID: CT-AMT-060-01	Table Shells			Final Version 05
Eddrac 1 No. 2013-00337942-42				Fage 39 01 00
Table 14.3.1.2 Frequency and Incidence of TEAEs b	y MedDRA SOC and PT - FAS			
SOC PT	Cohort 1 (N=x) n (%) E	Cohort 2 (N=x) n (%) E	Total (N=x) n (%) E	
Any TEAEs	x (xx.x) x	x (xx.x) x	x (xx.x) x	
Musculoskeletal and connective tissue disorders	x (xx.x) x	x (xx.x) x	x (xx.x) x	
Arthralgia	x (xx.x) x	x (xx.x) x	x (xx.x) x	
Musculoskeletal pain	x (xx.x) x	x (xx.x) x	x (xx.x) x	
Back pain	x (xx.x) x	x (xx.x) x	x (xx.x) x	
Pain in extremity	x (xx.x) x	x (xx.x) x	x (xx.x) x	
Neck pain	x (xx.x) x	x (xx.x) x	x (xx.x) x	
Joint swelling	x (xx.x) x	x (xx.x) x	x (xx.x) x	
Tenosynovitis	x (xx.x) x	x (xx.x) x	x (xx.x) x	
Infections and infestations	x (xx.x) x	x (xx.x) x	x (xx.x) x	
Nasopharyngitis	x (xx.x) x	x (xx.x) x	x (xx.x) x	
Sinusitis	x (xx.x) x	x (xx.x) x	x (xx.x) x	
Influenza	x (xx.x) x	x (xx.x) x	x (xx.x) x	
Rhinitis	x (xx.x) x	x (xx.x) x	x (xx.x) x	
	x (xx.x) x	x (xx.x) x	x (xx.x) x	
	x (xx.x) x	x (xx.x) x	x (xx.x) x	
	x (xx.x) x	x (xx.x) x	x (xx.x) x	
	x (xx.x) x	x (xx.x) x	x (xx.x) x	
	x (xx.x) x	x (xx.x) x	x (xx.x) x	

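### The adverse event overview shell (Table 14.3.1.1) labels unlikely-related events as adverse drug reactions and omits the combined related row that SAP 4.5.1 requires

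*SAP*

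**What the plan says.** SAP 4.5.1 sets the rule for relatedness: "An AE is considered related with the use of drug if the relationship to IMP is classified as either 'Probably related' or 'Possibly related". It then attaches the term at issue: "A related AE is referred to as an Adverse Drug Reaction (ADR". The same section lists the categories that the overview table is to contain, and "Related TEAEs" is one of them, as a single entry.

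The protocol agrees. Section 13.1 defines an ADR with the condition "A causal relationship between the IMP and the AE is at least a reasonable possibility". Section 13.2.2 describes the unlikely-related grade as "An AE with a temporal relationship to IMP administration which makes a causal relationship improbable".

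Shell 14.3.1.1, the overview table, is laid out differently. It has three causality rows: "Probably Related TEAEs (ADRs", "Possibly Related TEAEs (ADRs" and "Unlikely Related TEAEs (ADRs". It has no combined related row. Its footnote spells out the abbreviation ADR but does not redefine it. SAP section 7 makes the shell documents part of the SAP, so both the text and the shell are in force.

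**The concern.** The overview is the first summary of the primary endpoint in a first-in-human gene therapy trial. A reader who takes the row labels at face value would treat events that the investigator judged unlikely to be related as reactions to the vector.

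The same reader would want the number of subjects with at least one related event. The overview cannot give it, because a subject with both a probable and a possible event appears in two rows. SAP 4.5.1 asks for that number in this table, and the shell does not provide it.

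**Working it through.** The plan states no figure to reproduce. The check compares the shell with the definitions and then bounds what the missing row would have shown.

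**Step 1: the label, grade by grade.**

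| Causality grade (protocol 13.2.2) | ADR under SAP 4.5.1 | Labelled ADR in shell 14.3.1.1 |
|---|---|---|
| Probably related | Yes | Yes |
| Possibly related | Yes | Yes |
| Unlikely related | No | Yes |
| Not applicable | No | No row |

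Three of the three causality rows carry the label, where the SAP supports two. The protocol does not rescue the third. An ADR needs at least a reasonable possibility of causation, and the unlikely grade is defined by causation being improbable. TEAEs with missing causality are imputed as probably related under SAP 4.5.1, so their ADR label is consistent with the rule.

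**Step 2: the missing row, event counts.** If each event has one grade, related events = probable events + possible events. This can be read exactly from the first two rows.

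**Step 3: the missing row, subject counts.** Let a be the number of subjects with a probable event, b the number with a possible event, and N the cohort size. The number with any related event, R, satisfies

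max(a, b) ≤ R ≤ min(N, a + b).

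The lower limit applies when one group of subjects lies inside the other. The upper limit applies when the groups overlap as little as N allows.

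Take N = 5 (protocol 9.1), with assumed counts a = 2 and b = 3:

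- lower limit: max(2, 3) = 3, or 3/5 = 60%
- upper limit: min(5, 2 + 3) = 5, or 5/5 = 100%

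The gap is 2 subjects, or 40 percentage points. The gap is zero if a or b is zero.

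**Step 4: where the total does appear.** Shell 14.3.1.3 tabulates related TEAEs by system organ class and preferred term. Its footnote limits it to possibly and probably related events, and its first row gives subjects, percentage and events for any related TEAE, by cohort and overall. R is therefore planned, but in a different table from the overview.

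**The case against.** The strongest reply is that nothing is miscounted. Each grade has its own row, the row wording states the grade, and the ADR suffix looks as if it was carried one line too far. The combined subject count appears in Table 14.3.1.3 and can also be recovered from Listing 16.2.7.3, in a trial of about ten subjects. Counting a subject in more than one graded row is normal; the mild, moderate and severe rows of the same shell do it too. The primary endpoint is the frequency and incidence of adverse events, with no causality condition. No hypothesis is tested, and the stopping rules rest on causality judgements about individual events and not on this table.

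All of that stands, and it limits the size of the point. It does not remove the point: the label is still wrong under the plan's own definition, and a row that SAP 4.5.1 lists for this table is absent from it.

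Two stronger readings are tempting, and the documents support neither.

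- A reader might infer that the overview reports an inflated number of ADRs. It prints no pooled ADR figure. Such a number arises only if someone adds the unlikely row to the other two. The all-TEAE and severity rows carry no ADR label, and the not-applicable grade has no row.
- A reader might infer that Tables 14.3.1.1 and 14.3.1.3 give conflicting results. Table 14.3.1.3 does not use the term ADR, and the probable and possible event counts in the overview add up to its related total. The conflict is between a label and a definition.

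**Conclusion.** The point holds as a minor internal inconsistency: one mislabelled row and one omitted row in shell 14.3.1.1. The analysis rule in SAP 4.5.1 is clear and correct, and the individual row counts would be right as planned.

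What the overview loses is the number of subjects with any related event. In the illustration for a cohort of 5, that number is left uncertain by 2 subjects; those counts are assumed and are not trial data. The conclusion rests on the shells being part of the SAP, as section 7 states, and on the row labels being final text. It is worth correcting because the table summarises the primary safety endpoint and the SAP already specifies the right content.

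**What to change.** In shell 14.3.1.1:

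1. Remove the ADR suffix from the unlikely-related row.
2. Add one row for related TEAEs (ADRs), defined as probably or possibly related after the SAP 4.5.1 imputation, with each subject counted once.
3. Keep the probable and possible rows as indented sub-rows beneath it.
4. Add a programming check that the new row equals the any-related row of Table 14.3.1.3 for subjects and events, in each cohort and overall.

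The cost is an edit to one shell and its table program. No data, definition or method changes.

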14.3.7 Other Safety Observations Displays

Sponsor: uniQure biopharma B.V	Date 27MAY2021			larix
Trial ID: CT-AMT-060-01 EudraCT No: 2013-00557942-42	Table Shells			Final Version 05 Page 55 of 66
Table 14.3.7.1 Summary of concomitant medications (Other	than FIX replacement ther	apy) by therapeut	ic grouping - Full ar	alysis set
ATC level 1 ATC level 2	Cohort 1 (N=x) n (%) E	Cohort 2 (N=x) n (%) E	Total (N=x) n (%) E	
Any medication	x (xxx) x	x (xxx) x	x (xxx) x	
Alimentary Tract And Metabolism Drugs For Acid Related Disorders	x (xxx) x x (xxx) x	x (xxx) x	x (xxx) x	
Drugs Used In Diabetes	x (xxx) x	x (xxx) x	x (xxx) x	
Drugs For Constipation	x (xxx) x	x (xxx) x	x (xxx) x	
Antidiarrheals, Intestinal Antiinflammatory/Antiin	x (xxx) x	x (xxx) x	x (xxx) x	
Antiemetics And Antinauseants	x (xxx) x	x (xxx) x	x (xxx) x	
Drugs For Functional Gastrointestinal Disorders	x (xxx) x	x (xxx) x	x (xxx) x	
Vitamins	x (xxx) x	x (xxx) x	x (xxx) x	
Stomatological Preparations	x (xxx) x	x (xxx) x	x (xxx) x	
Nervous System	x (xxx) x	x (xxx) x	x (xxx) x	
Analgesics	x (xxx) x	x (xxx) x	x (xxx) x	
Psycholeptics	x (xxx) x	x (xxx) x	x (xxx) x	
Anesthetics	x (xxx) x	x (xxx) x	x (xxx) x	
Cardiovascular System	x (xxx) x	x (xxx) x	x (xxx) x	
Agents Acting On The Renin-Angiotensin System	x (xxx) x	x (xxx) x	x (xxx) x	
Lipid Modifying Agents	x (xxx) x	x (xxx) x	x (xxx) x	
Beta Blocking Agents	x (xxx) x	x (xxx) x	x (xxx) x	

N: Number of patients in Full Analysis Set (FAS). ATC Class: Anatomical Therapeutic Chemical Classification.

n: Number of patients with the medication. (%): Percentage of patients with the medication in FAS. E: Number of Medications.

Cohort 1: AAV5-hFIX 5.0 x 10^12 gc/kg, Cohort 2: AAV5-hFIX 2.0 x 10^13 gc/kg

Medication coded with WHO DD version 143E

Sponsor: uniQure biopharma B.V	Date 27MAY2021			larix
Trial ID: CT-AMT-060-01 EudraCT No: 2013-00557942-42	Table Shells			Final Version 05 Page 56 of 66
Table 14.3.7.1 Summary of concomitant medications (Other than FIX replaced)	cement therapy) by therapeutic grouping	g - Full analysis set		
ATC level 1 ATC level 2	Cohort 1 (N=x) n (%) E	Cohort 2 (N=x) n (%) E	Total (N=x) n (%) E	
Diuretics	x (xxx) x	x (xxx) x	x (xxx) x	
Calcium Channel Blockers	x (xxx) x	x (xxx) x	x (xxx) x	
Antiinfectives For Systemic Use	x (xxx) x	x (xxx) x	x (xxx) x	
Antibacterials For Systemic Use	x (xxx) x	x (xxx) x	x (xxx) x	
Antivirals For Systemic Use	x (xxx) x	x (xxx) x	x (xxx) x	
Vaccines	x (xxx) x	x (xxx) x	x (xxx) x	
Systemic Hormonal Preparations, Excl. Sex Hormones	x (xxx) x	x (xxx) x	x (xxx) x	
Concosterolus Foi Systemite Ose	x (xxx) x	x (xxx) x	x (xxx) x	
Musculo-Skeletal System	x (xxx) x	x (xxx) x	x (xxx) x	
Antiinflammatory And Antirheumatic Products	x (xxx) x	x (xxx) x	x (xxx) x	
Muscle Relaxants	x (xxx) x	x (xxx) x	x (xxx) x	
Blood And Blood Forming Organs	x (xxx) x	x (xxx) x	x (xxx) x	
Antihemorrhagics	x (xxx) x	x (xxx) x	x (xxx) x	
Blood Substitutes And Perfusion Solutions	x (xxx) x	x (xxx) x	x (xxx) x	
Respiratory System	x (xxx) x	x (xxx) x	x (xxx) x	
Drugs For Obstructive Airway Diseases	x (xxx) x	x (xxx) x	x (xxx) x	

N: Number of patients in Full Analysis Set (FAS). ATC Class: Anatomical Therapeutic Chemical Classification.

n: Number of patients with the medication. (%): Percentage of patients with the medication in FAS. E: Number of Medications.

Cohort 1: AAV5-hFIX 5.0 x 10^12 gc/kg, Cohort 2: AAV5-hFIX 2.0 x 10^13 gc/kg

Medication coded with WHO DD version 143E

Sponsor: uniQure biopharma B.V	Date 27MAY2021			larix
Trial ID: CT-AMT-060-01				Final Version 05
Ludiaci no. 2013-00337942-42				Fage 57 01 00
Table 14.3.7.1 Summary of concomitant medications (Other	er than FIX replacement therapy) by therapeutic grouping	g - Full analysis set		
ATC level 1	Cohort 1	Cohort 2	Total	
A LU JEVEL I	118-51	(N=X)	1 1 - 1 1	
ATC level 1 ATC level 2	n (%) E	n (%) E	n(%) E	
ATC level 2 Nasal Preparations	$\frac{\mathbf{n}(\mathbf{\%}) \mathbf{E}}{\mathbf{x}(\mathbf{x}\mathbf{x}) \mathbf{x}}$	n = x n (%) = E x (xxx) x	(1-x) n (%) E x (xxx) x	_

Ophthalmological And Otological Preparations	x (xxx) x	x (xxx) x	x (xxx) x
Genito Urinary System And Sex Hormones	x (xxx) x	x (xxx) x	x (xxx) x
Urologicals	x (xxx) x	x (xxx) x	x (xxx) x
***** ATC1 not coded *****	x (xxx) x	x (xxx) x	x (xxx) x
***** ATC2 not coded *****	x (xxx) x	x (xxx) x	x (xxx) x
Antineoplastic And Immunomodulating Agents	x (xxx) x	x (xxx) x	x (xxx) x
Antineoplastic Agents	x (xxx) x	x (xxx) x	x (xxx) x

N: Number of patients in Full Analysis Set (FAS). ATC Class: Anatomical Therapeutic Chemical Classification.

n: Number of patients with the medication. (%): Percentage of patients with the medication in FAS. E: Number of Medications.

Cohort 1: AAV5-hFIX 5.0 x 10^12 gc/kg, Cohort 2: AAV5-hFIX 2.0 x 10^13 gc/kg

Medication coded with WHO DD version 143E

Sponsor: uniQure biopharma B.V		Date 27MAY2021		larix
Trial ID: CT-AMT-060-01 FudraCT No: 2013-00557942-42		Table Shells		Final Version 05 Page 58 of 66
				1 490 00 01 00
Table 14.3.7.2 Summary of tir	ne to first shedding ne	gative (days) - Vector DNA - F	ull analysis set	
	Cohort 1 (N=x)	Cohort 2 (N=x)	Total (N=x)	
Vector DNA Blood (copies/mL)				
n	x (xxx) x	x (xxx) x	x (xxx) x	
Mean (SD)	x (xxx) x	x (xxx) x	x (xxx) x	
Median	x (xxx) x	x (xxx) x	x (xxx) x	
Min ; Max	x (xxx) x	x (xxx) x	x (xxx) x	
Vector DNA Faeces (copies/mg)				
n	x (xxx) x	x (xxx) x	x (xxx) x	
Mean (SD)	x (xxx) x	x (xxx) x	x (xxx) x	
Median	x (xxx) x	x (xxx) x	x (xxx) x	
Min ; Max	x (xxx) x	x (xxx) x	x (xxx) x	
Vector DNA Nasal Secretion (copies po	er swab)			
n	x (xxx) x	x (xxx) x	x (xxx) x	
Mean (SD)	x (xxx) x	x (xxx) x	x (xxx) x	
Median	x (xxx) x	x (xxx) x	x (xxx) x	
Min ; Max	x (xxx) x	x (xxx) x	x (xxx) x	
Vector DNA Saliva (copies/mL)				
n	x (xxx) x	x (xxx) x	x (xxx) x	
Mean (SD)	x (xxx) x	x (xxx) x	x (xxx) x	
Median	x (xxx) x	x (xxx) x	x (xxx) x	
Min ; Max	x (xxx) x	x (xxx) x	x (xxx) x	

N: Number of patients in Full Analysis Set (FAS). n: Number of patients who have met the criterion for shedding negative.

First shedding negative is defined for a specific matrix when 3 consecutive negative samples have been detected for the patient for that particular type of matrix.

Cohort 1: AAV5-hFIX 5.0 x 10^12 gc/kg, Cohort 2: AAV5-hFIX 2.0 x 10^13 gc/kg

UniQure/AMT/CT-AMT-060-01/current - tab\_shed\_neg.sas/tab\_shed\_neg.rtf/10jan2018

Sponsor: uniQure biopharma B.V Trial ID: CT-AMT-060-01		Date 27MAY2021		Final Version 05
EudraCT No: 2013-00557942-42		Table Shells		Page 59 of 66
Table 14.3.7.2 Summary of time to first	shedding negative (days) - Vo	ector DNA - Full analysis set		
	Cohort 1 (N=x)	Cohort 2 (N=x)	Total (N=x)	
Vector DNA Semen (copies/mL)				
n	x (xxx) x	x (xxx) x	x (xxx) x	
Mean (SD)	x (xxx) x	x (xxx) x	x (xxx) x	
Median	x (xxx) x	x (xxx) x	x (xxx) x	
Min ; Max	x (xxx) x	x (xxx) x	x (xxx) x	
Vector DNA Urine (copies/mL)				
n	x (xxx) x	x (xxx) x	x (xxx) x	
Mean (SD)	x (xxx) x	x (xxx) x	x (xxx) x	
Median	x (xxx) x	x (xxx) x	x (xxx) x	
Min ; Max	x (xxx) x	x (xxx) x	x (xxx) x	

N: Number of patients in Full Analysis Set (FAS). n: Number of patients who have met the criterion for shedding negative.

First shedding negative is defined for a specific matrix when 3 consecutive negative samples have been detected for the patient for that particular type of matrix.

Cohort 1: AAV5-hFIX 5.0 x 10^12 gc/kg, Cohort 2: AAV5-hFIX 2.0 x 10^13 gc/kg

UniQure/AMT/CT-AMT-060-01/current - tab\_shed\_neg.sas/tab\_shed\_neg.rtf/10jan2018

 Sponsor: uniQure biopharma B.V
 Date 27MAY2021

 Trial ID: CT-AMT-060-01
 Final Version 05

 EudraCT No: 2013-00557942-42
 Table Shells

